- External monitoring is performed by an independent Clinical Research Associate (CRA), which provides regular site monitoring and data validation to ensure data quality and patient safety.
- The Data Safety Monitoring Board (DSMB) periodically reviews accumulated safety data, including adverse event frequencies and severity, to address any unexpected risks promptly.

Substudies

The following substudies are planned:

- Echocardiographic substudy,
- Magnetic Resonance Imaging substudy.

Subgroup analysis

The analysis of the following subgroups is planned in the study:

- Women versus men,
- Patients with prehospital time delay duration 3 hours and longer versus less than 3 hours,
- Patients with and without out-of-hospital cardiac arrest,
- Patients with and without mechanical ventilation,
- Patients with and without mechanical circulatory support (e.g., IMPELLA, ECMO)*
- Patients with and without persistent coma (Glasgow Coma Scale < 8) at admission,
- Patients with and without diabetes,
- Patients with and without obesity,
- Patients who are cigarette smokers versus non-smokers,
- Patients with and without multivessel disease,
- Patients with and without a history of heart failure.

**A time-dependent covariate analysis will be performed instead of standard subgroup analysis to prevent bias due to treatment-dependent selection effects for mechanical circulatory support (MCS), which may occur post-randomization.*

Handling of Post-Randomization Events (MCS)

MCS use will be modeled as time-dependent covariates in survival analyses to avoid bias introduced by post-randomization treatment effects. These covariates will be introduced into the primary and secondary outcome models as follows:

Time-Dependent Covariate Analysis

To accurately account for the influence of MCS on study outcomes, these variables will be modeled as time-dependent covariates within the Cox proportional hazards model:

Primary Model:

- $HR = \beta_1(\text{Treatment}) + \beta_2(\text{Mechanical Ventilation (time-dependent)}) + \beta_3(\text{ECMO (time-dependent)}) + \epsilon$
- This ensures that the estimation of treatment effects is not confounded by patients who deteriorate and need additional support after randomization.

Competing Risks Model (Fine & Gray) for Non-MACE Outcomes:

- If MCS is strongly associated with mortality before the primary endpoint, a competing risks approach will be applied using the Fine & Gray subdistribution hazard model.

Sensitivity Analysis

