The analysis of the primary and secondary endpoints in the complete study population assumes a balanced distribution of potentially confounding factors between the study arms, which is expected to be achieved through randomization. Considering this assumption, no prior planned multivariate adjustment for the confounding variables will be conducted in the initial analysis of the primary endpoints. However, despite this, further exploratory analyses will incorporate both univariate and multivariate models, such as logistic regression and Cox proportional hazards models, to evaluate the potential influence of specific patient characteristics on the occurrence of the endpoints. This approach will provide a more detailed understanding of how individual baseline factors may affect study outcomes. Additionally, time-to-event data will be visualized using the Kaplan-Meier methodology, allowing for an informative representation of the temporal aspects of endpoint occurrences. Time to the event will be computed from the date of randomization and the date of the analyzed event or the date of last contact in the case of censored patients.

For subgroup analyses, where confounding factors may exhibit an unbalanced distribution across the study arms, they will be incorporated into the multivariate logistic regression models. This will allow for appropriate adjustment for these confounders, providing a more accurate estimation of the association between treatment effects and study endpoints in the presence of imbalances. By accounting for such factors, the analysis will enhance the robustness and validity of the conclusions drawn regarding the study outcomes within the specified subgroups.

Safety analysis

This phase IV clinical trial focuses on observing and comparing the use of approved medicinal products as part of standard clinical practice. Information regarding side effects will neither be actively collected nor evaluated.

Hospitalizations and life-threatening conditions, which are prerequisites for study enrollment, are not categorized as serious adverse events (SAEs). The investigator will perform causality assessments, and immediate reporting of adverse events unrelated to the study will not be required.

In routine clinical practice, cardiogenic shock has a mortality rate of over 50%. Deaths unrelated to the study will be summarized and included in annual study reports.

References

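### The time-dependent Cox model for mechanical circulatory support has no term for IMPELLA or for any-device support, and its formula is misprinted

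*SAP*

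**What the plan says.** The SAP's Subgroup analysis section lists "Patients with and without mechanical circulatory support (e.g., IMPELLA, ECMO" as one item, with a footnote. The footnote replaces the usual subgroup comparison for MCS with a time-dependent covariate analysis, because support may start after randomization and may depend on treatment. The same list has a separate item, "Patients with and without mechanical ventilation", without that footnote.

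Under Handling of Post-Randomization Events (MCS), the SAP states: "MCS use will be modeled as time-dependent covariates in survival analyses to avoid bias introduced by post-randomization treatment effects". It adds that these covariates go into the models for the primary and secondary outcomes. Under Time-Dependent Covariate Analysis it says that "these variables will be modeled as time-dependent covariates within the Cox proportional hazards model", and prints an equation headed Primary Model. The left side and first term are "HR = \beta_1(\text{Treatment". The two time-dependent terms are "Mechanical Ventilation (time-dependent" and "ECMO (time-dependent", and the equation ends with an additive error term.

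The next two subsections refer to MCS in general. Sensitivity Analysis plans inverse probability weighting for differences between patients who do and do not require MCS. Reporting & Interpretation splits the Kaplan-Meier curves by whether MCS was required and confines formal testing to time-dependent Cox models.

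**The concern.** The text announces a model of MCS use, but the equation contains only one of the two devices that the SAP names. It has no general MCS indicator. Its other time-dependent term, ventilation, is not among the SAP's examples of MCS. A programmer who follows the equation fits an ECMO-and-ventilation model. A programmer who follows the text fits an MCS model. The coefficients and the adjusted treatment effect would differ between the two.

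At stake is the only formal comparison that the SAP plans for MCS. It would use a narrower exposure than the curves and the weighted analysis that it is meant to accompany. Separately, the equation as printed is not a Cox model.

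**Working it through.** The SAP gives no sample size, power or event count for this model, so there is no figure to reproduce. The check has three steps.

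**1. Covariates against the SAP's own description of MCS.** Code a patient while on support, first by the printed terms and then by an any-device indicator:

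| Support | Printed: ventilation | Printed: ECMO | Any-device MCS(t) |
|---|---|---|---|
| None | 0 | 0 | 0 |
| ECMO alone | 0 | 1 | 1 |
| IMPELLA alone | 0 | 0 | 1 |
| Ventilation alone | 1 | 0 | 0 |
| IMPELLA and ventilation | 1 | 0 | 1 |

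Under the printed terms, IMPELLA alone is coded like no support, and IMPELLA with ventilation is coded like ventilation alone. Under the wording of Sensitivity Analysis and Reporting & Interpretation, both IMPELLA patients belong with those who required MCS. No other section of the SAP extends the ECMO term to other devices or says that ventilation counts as MCS. Ventilation on admission is recorded at randomization and listed again under Description of patients' characteristics.

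**2. Form of the equation.** A Cox model with these covariates is

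h(t) = h0(t) exp{b1·Treatment + b2·x2(t) + b3·x3(t)},

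so the linear sum equals the log hazard ratio, with no error term. To show the difference, assume hazard ratios of 0.8 for treatment and 3 for ECMO. These values are illustrative and not from the SAP. Then b1 = ln 0.8 = -0.223 and b3 = ln 3 = 1.099.

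| Patient | Printed sum, read literally as HR | Cox HR |
|---|---|---|
| Control, no support | 0 | exp(0) = 1.0 |
| Treated, no support | -0.223 | 0.8 |
| Control, ECMO | 1.099 | 3.0 |
| Treated, ECMO | ln 0.8 + ln 3 = ln 2.4 = 0.875 | 0.8 × 3 = 2.4 |

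Over assumed treatment hazard ratios of 0.6, 0.7, 0.8, 0.9 and 1.0, the literal value for a treated patient without support is -0.511, -0.357, -0.223, -0.105 and 0. A hazard ratio cannot be zero or negative.

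**3. Status of the model.** The SAP's Statistical analysis section assigns the endpoints to the chi-square test and non-inferiority to a one-sided Z-test. Additional analyses plans no covariate adjustment in the initial analysis of the primary endpoints and describes Cox models as exploratory. The heading Primary Model, together with the statement that the MCS covariates enter the primary outcome models, does not fit with that.

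**The case against.** The strongest reply is that the equation is loose notation. The text names the Cox model, and standard Cox software fits the log-hazard form whatever the SAP prints. That stands: the misprint alone would not produce wrong results, and the impossible values above come from a reading that nobody would program. The missing IMPELLA term is different, because software fits the covariates it is given.

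It can also be said that an IMPELLA-only patient is correctly coded as having no ECMO. That is true. IMPELLA is omitted, not miscoded. The omission still conflicts with the stated aim of modelling MCS use, and the abbreviation e.g. in the subgroup list widens MCS beyond ECMO where the equation narrows it.

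A reader might infer that ventilation was put in as a substitute for IMPELLA, or that it has to come out. The SAP says neither. The section's stated purpose, patients who deteriorate and need more support, can cover ventilation, and having its own subgroup does not bar it from a time-dependent model. What is missing is a reason for it under an MCS heading.

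A reader might also infer that a device start and an event on the same day cannot be ordered, since Additional analyses says "Time to the event will be computed from the date of randomization and the date of the analyzed event". That sentence defines time to event. It does not say how device start is recorded or that clock times are unavailable, so the conclusion does not follow.

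Finally, Primary Model may mean primary within the MCS section, as against the competing-risks and sensitivity analyses after it. That is plausible, but the statement about the primary outcome models leaves it open.

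**Conclusion.** The point holds as an inconsistency in a supporting analysis: the printed Cox model does not model MCS as the SAP describes it. The misprinted formula is a secondary error. Severity is minor.

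Its size cannot be stated in patients, because the number supported by IMPELLA without ECMO is not given; all of them would have no MCS exposure in the model. The conclusion assumes that the equation is programmed with the covariates as printed.

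A reader might take this as a flaw in the trial's main result. The SAP does not support that, because the main endpoint tests are unadjusted and do not use this model.

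**What to change.** Replace the equation with

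h(t) = h0(t) exp{b1·Treatment + b2·MCS(t)},

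where MCS(t) = 1 from the start of any circulatory support device (IMPELLA, ECMO or other) and 0 before. Alternatively, use separate time-dependent terms for IMPELLA and ECMO. Drop the error term. Use the same definition of MCS for the Kaplan-Meier curves and the weighted analysis.

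If time-dependent ventilation is kept, list it as an additional covariate, not as MCS, and give the reason. Label the model supportive instead of primary, in line with Statistical analysis and Additional analyses.

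This brings the model into line with the SAP's own description and does no more than that. It still adjusts for support that treatment may influence, and it has no treatment-by-MCS term, so it does not estimate a subgroup effect.

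The cost is a few lines of SAP text and one derived variable, assuming that device type and start are recorded. The SAP does not show those fields. Trial conduct does not change.

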5. Women of childbearing potential should be protected from pregnancy throughout the study (relevant for long-term use of ticagrelor). Suitable methods of contraception, in this case, include hormonal contraceptives, barrier methods, or complete withdrawal – as long as it is consistent with the patient's lifestyle.

Exclusion criteria

1. Contraindications to antiplatelet therapy with ticagrelor/cangrelor:
 - Recent (< 6 months) major bleeding,
 - Recent (< 1 month) major surgery/injury,
 - History of intracranial hemorrhage,
 - History of Stroke/TIA,
 - Known ticagrelor/cangrelor intolerance,
 - Severe hepatic impairment,
 - Co-administration of potent CYP3A4 inhibitors (e.g., ketoconazole, clarithromycin, nefazodone, ritonavir, and atazanavir).

2. Administration of a loading dose of oral P2Y₁₂ inhibitor before admission (clopidogrel ≥ 300 mg, ticagrelor 180 mg, prasugrel 60 mg).
3. Need for concomitant chronic anticoagulant treatment due to atrial fibrillation, artificial valve, thromboembolic disease, etc.

Study endpoints

Primary endpoint – laboratory

- Comparison of the effect of parenteral cangrelor with the recommended crushed ticagrelor treatment on periprocedural ADP-activated platelet aggregation; the periprocedural rate of onset and the proportion of patients who achieve effective* P2Y₁₂ platelet receptor inhibition defined by a Platelet Reactivity Index (PRI) value at the end of percutaneous coronary intervention.

**Platelet Reactivity Index (PRI) less than 50% as measured by the vasodilator-stimulated phosphoprotein (VASP) phosphorylation flow cytometric assay*

Primary endpoint – clinical

- Comparison of the effect of parenteral cangrelor with the recommended crushed ticagrelor treatment on the incidence of major cardiovascular events 30 days after enrollment in the study. The primary clinical endpoint is a composite of all-cause death, myocardial infarction, or stroke* within 30 days, expressed as a proportion of patients with any of these events. The primary clinical endpoint is non-inferiority, and if this is met, then superiority will be tested.

**Ischemic stroke (intracranial hemorrhage assessed as a BARC 3c bleeding)*

Secondary endpoints

Key secondary efficacy endpoint

- Death, myocardial infarction, urgent revascularization of the infarct-related artery, stent thrombosis, or ischemic stroke within 30 days and one year after study enrollment expressed as a proportion of patients with any of these events.

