Key secondary safety endpoint

- Occurrence of bleeding, as defined by BARC type ≥ 3B, within 30 days and one year after study enrollment expressed as a proportion of patients with any of these events.

Other secondary endpoints

The following endpoints will be expressed as the proportion of patients with events:

- Death, myocardial infarction, urgent revascularization of the infarct-related artery, stroke, or major bleeding as defined by the BARC (Bleeding Academic Research Consortium) criteria* on day 30 and one year after study enrollment expressed as a proportion of patients with any of these events.

**BARC type $\geq 3B$*

- Cardiovascular death, myocardial infarction, urgent revascularization, and heart failure on day 30 and one year after study enrollment.
- Individual components of the primary clinical endpoint on day 30 and one year after study enrollment.
- Heart failure* on day 30 and one year after study enrollment.

**New heart failure or hospitalization for heart failure*

- Cardiovascular death on day 30 and one year after study enrolment.
- Occurrence of bleeding as defined by BARC type $\geq 3B$ within 30 days after study enrolment.
- Occurrence of stent thrombosis within 30 days after study enrolment.
- Delayed* aortocoronary bypass surgery due to a risk of bleeding within 30 days after study enrolment.

**Assessed by the heart team, indicating aortocoronary bypass surgery.*

- Effective* P2Y₁₂ platelet receptor inhibition defined by Platelet Reactivity Index (PRI) value 1 hour after PCI.

**Platelet Reactivity Index (PRI) less than 50% as measured by the vasodilator-stimulated phosphoprotein (VASP) phosphorylation flow cytometric assay*

The following endpoints will be displayed as the median and interquartile range (IQR):

- Duration of vasoactive pharmacotherapy and/or mechanical circulatory support in days.
- Duration of hospitalization* in days.

**Intensive care unit stay and total hospital stay*

- Maximum values of high-sensitive cardiac troponin in μg per liter.

Other pursued goals

- Cost-effectiveness is expressed as a comparison of the costs of treatment (including days of hospitalization, ICU stays, medical procedures, and pharmacotherapy) and its effect on the occurrence of endpoints. This is measured as the cost per avoided event up to day 30 and up to 1 year after randomization.

Sample size calculation

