- Inverse Probability of Treatment Weighting (IPTW) will be applied as an alternative approach to adjusting for potential differences between patients requiring MCS and those who do not.

Reporting & Interpretation

- The Kaplan-Meier curves for MACE outcomes will be stratified based on whether patients required MCS, but formal statistical comparisons will be limited to time-dependent Cox models to avoid survivor bias.
- Forest plots will be presented for pre-randomization subgroups only.

Analysis population

The patients enrolled in the study will be summarized in a CONSORT flow diagram. The analyses will be conducted using a modified intention-to-treat principle (MITT), an intention-to-treat principle (ITT), and a per-protocol (PP) approach. The MITT population includes all randomized patients in the trial who received a dose of the study drug. The ITT encompasses all trial-randomized patients, and the PP population consists of all randomized patients who received the full dose of the study drug as per protocol. Treatment classification in all scenarios will be based on the randomized treatment. The MITT will serve as the primary analysis approach; analyses based on ITT and PP populations will be considered secondary and confirmatory.

Data Sharing

The data used in the published scientific papers will be available according to the requirements of the respective scientific journals. To mitigate the risk to patient privacy, the data will be

anonymized and identified through masking or generalization of direct and some indirect identifiers. Only variables used in the given analysis will be included in the shared dataset.

Statistical analysis

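### The Fine & Gray rule hangs on a void and irrelevant MCS condition, which leaves Kaplan-Meier as the only named display for outcomes that exclude all-cause death

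*SAP*

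**What the plan says.** - SAP, Handling of Post-Randomization Events (MCS): a line headed "Competing Risks Model (Fine & Gray) for Non-MACE Outcomes" is followed by the condition "If MCS is strongly associated with mortality before the primary endpoint, a competing risks approach will be applied". No criterion for the strength of the association is given.
- SAP, Study endpoints: "The primary clinical endpoint is a composite of all-cause death, myocardial infarction, or stroke* within 30 days". The other primary endpoint is a laboratory one, "defined by a Platelet Reactivity Index (PRI) value at the end of percutaneous coronary intervention".
- SAP, Other secondary endpoints: the list includes "Individual components of the primary clinical endpoint on day 30 and one year after study enrollment", as well as BARC type 3B or higher bleeding, stent thrombosis, heart failure and cardiovascular death. These are expressed as proportions of patients with events.
- SAP, Statistical analysis: endpoints are tested by chi-square and described by relative risks with 95% confidence intervals.
- SAP, Additional analyses: "time-to-event data will be visualized using the Kaplan-Meier methodology". Time runs from randomization to the event or to "the date of last contact in the case of censored patients". Death as a competing event is not mentioned.
- SAP, Reporting & Interpretation: "The Kaplan-Meier curves for MACE outcomes will be stratified based on whether patients required MCS".

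**The concern.** The line heading shows that the authors saw a need for competing-risks methods outside MACE. The condition attached to it does not meet that need, for three reasons.

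1. A death within 30 days is itself the clinical primary endpoint, so it cannot come before it.
2. Without a threshold, the choice of method would be made after seeing the data.
3. Whether death removes a patient from the risk of later bleeding or stent thrombosis does not depend on whether MCS predicts death.

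If the rule does not fire, the SAP names only Kaplan-Meier curves and Cox models for time-to-event work. In a population where about half may die within 30 days, a Kaplan-Meier curve for a non-fatal outcome with deaths censored does not show the share of patients who have the event. It shows a larger figure. The key safety endpoint, BARC type 3B or higher bleeding, is one of the outcomes exposed to this if it is plotted.

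**Working it through.** **The plan's own figure.** The SAP gives no figure for competing risks. Its event rates enter the superiority sample size, which reproduces. With 50% vs 38%, two-sided 0.05, power 0.8 and no continuity correction, n per arm = [1.96·√(2·0.44·0.56) + 0.8416·√(0.50·0.50 + 0.38·0.62)]² / 0.12² = 3.851/0.0144 = 267.4. That rounds up to 268 per arm, or 536 in total, as stated. Nothing below alters it.

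**Inputs.** The 30-day mortality of 43.3% and 51.5% comes from the trial cited under Sample size calculation. The Safety analysis section also puts mortality in routine practice above 50%. The non-fatal incidences of 5% and 10% are illustrative and are not in the SAP. Deaths are assumed to be censored at the date of death, since the SAP has no rule for them.

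**Proportional hazards.** Let c be the true 30-day cumulative incidence of the non-fatal event and m the proportion who die without having had it. Then H = −ln(1 − c − m), the event's share is He = H·c/(c + m), and the plotted value is 1 − exp(−He).

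| m | c | H | He | 1−KM | 1−KM / c |
|---|---|---|---|---|---|
| 43.3% | 5% | 0.660 | 0.0683 | 6.6% | 1.32 |
| 51.5% | 5% | 0.832 | 0.0737 | 7.1% | 1.42 |
| 43.3% | 10% | 0.761 | 0.1429 | 13.3% | 1.33 |
| 51.5% | 10% | 0.954 | 0.1552 | 14.4% | 1.44 |

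If m is instead read as overall mortality and the event is rare, the ratio is −ln(1 − m)/m. That gives 0.5674/0.433 = 1.31 and 0.7236/0.515 = 1.41. Taken together, the overstatement is about 30% to 45%.

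**Different timing.** Let the cumulative hazards follow Weibull shapes k for death and j for the event, with time scaled to 30 days and Hd = −ln(1 − m). For a rare event the ratio is 1 / ∫₀¹ j·t^(j−1)·exp(−Hd·t^k) dt.

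- Events early, deaths spread evenly (k = 1, j = 0.3): 1.13 at 43.3% and 1.16 at 51.5%.
- Deaths early, events spread evenly (k = 0.3, j = 1): 1.54 at 43.3% and 1.73 at 51.5%.

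So the overstatement runs from about 10% to about 70%. It is positive in every pattern tried.

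**What is not affected.** In a simulation with 45% mortality and complete follow-up, the crude proportion with the non-fatal event was 4.40% and 1−KM was 5.85% (ratio 1.33). The crude proportion is the quantity wanted. For the composite that includes death, the proportion and 1−KM were both 48.3%.

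**Cardiovascular death.** Only non-cardiovascular death competes here, so the overstatement would be smaller than the figures above. The SAP gives no rate from which to size it.

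**The case against.** The strongest reply is that little rests on these curves. The clinical endpoints are analysed as proportions, with chi-square tests and relative risks. With complete follow-up, a crude proportion already equals the cumulative incidence with death competing. Kaplan-Meier appears under Additional analyses and only as a visualization. The one place where the SAP names outcomes for such curves is MACE, and a composite containing all-cause death has no bias. The SAP also never says that bleeding or stent thrombosis will be plotted this way, or that deaths will be censored. All of this stands, and it limits the point to a supportive display.

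A reader might infer more, in four ways that the SAP does not support.

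- That the trial's reported non-fatal event rates, or the comparison of bleeding between arms, will be inflated by a third. The planned estimates are proportions and relative risks, so they are not.
- That the trigger can never be met. This is true for the clinical primary endpoint, but a death can precede the laboratory one, measured at the end of PCI. The phrase might also loosely mean before day 30. Neither reading rescues the rule: a platelet index is not a survival outcome, and the MCS condition stays irrelevant with no threshold.
- That a Cox model with deaths censored is wrong. Censoring removes the dead from the risk set, and the model validly estimates a cause-specific hazard ratio. The error lies in reading that ratio, or 1−KM, as absolute risk.
- That the arms would be made to look materially different. If the planned composite rates of 50% and 38% stand in for mortality, equal true incidences of 5% plot as 7.0% and 6.3%, and equal true incidences of 10% as 14.2% and 12.7%. The spurious gap of about 0.7 to 1.4 points (before rounding) is below one standard error of a difference at 268 per arm: √(2·0.05·0.95/268) = 1.9 points and √(2·0.10·0.90/268) = 2.6 points.

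**Conclusion.** The point holds in a limited form. The condition for Fine & Gray is void for the clinical primary endpoint, has no threshold, and depends on something that has no bearing on whether death competes. This is a rule stated wrongly, not detail left to another document. Its consequence is confined to Kaplan-Meier displays of outcomes that exclude all-cause death. At 43.3% to 51.5% mortality, such curves would overstate 30-day risk by about 30% to 45% under proportional hazards, and by about 10% to 70% over the timing patterns tried. These sizes assume that deaths are censored and that mortality resembles the cited trial. They do not apply to cardiovascular death, where the effect is smaller, or to the one-year curves, for which the SAP gives no mortality. The primary test, the key secondary tests, the relative risks and the sample size do not change.

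**What to change.** Delete the MCS condition. State that, in every time-to-event analysis of an outcome that excludes all-cause death, death is a competing event. For cardiovascular death, and for the composite that contains it instead of all-cause death, the competing event is non-cardiovascular death. For these outcomes:

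- plot Aalen-Johansen cumulative incidence in place of one minus Kaplan-Meier;
- report the cause-specific hazard ratio from a Cox model with deaths censored, labelled as such;
- give the Fine & Gray model as supportive.

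Keep Kaplan-Meier for all-cause death and for composites that contain it. Leave the proportions, chi-square tests and relative risks as planned.

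The cost is a change of wording and a small amount of extra analysis, possibly with software beyond the named SPSS version. No new data are needed.

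### Time-dependent MCS appears to enter a Fine & Gray model that keeps dead patients at risk, so its coefficient depends on mortality and on an unstated coding after death

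*SAP*

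**What the plan says.** The SAP section Handling of Post-Randomization Events (MCS) opens with a general rule: "MCS use will be modeled as time-dependent covariates in survival analyses to avoid bias introduced by post-randomization treatment effects". It continues: "These covariates will be introduced into the primary and secondary outcome models as follows". Two models follow. The first is a Cox model with treatment, mechanical ventilation and ECMO, the last two time-dependent. The second is headed "Competing Risks Model (Fine & Gray) for Non-MACE Outcomes" and has a condition: "If MCS is strongly associated with mortality before the primary endpoint", then "a competing risks approach will be applied using the Fine & Gray subdistribution hazard model".

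The Fine & Gray item does not list its covariates, name the outcomes or the competing event, or set a threshold for a strong association. It does not say what MCS value a patient has after death. Its trigger speaks of mortality before the primary endpoint, although under Study endpoints all-cause death is itself part of that endpoint.

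Under Reporting & Interpretation, in a sentence about Kaplan-Meier curves for MACE, the SAP adds that "formal statistical comparisons will be limited to time-dependent Cox models to avoid survivor bias".

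**The concern.** In a Fine & Gray model a patient who dies without the outcome stays in the risk set to the end of follow-up. That is workable for a covariate fixed at randomization. MCS is different: it is observed only while the patient lives. To fit the model, someone must assign MCS values to the dead, and the estimate depends on what is assigned.

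This matters here for two reasons. The Safety analysis section says that "cardiogenic shock has a mortality rate of over 50" percent, so dead patients would become a large part of the risk set. And the model is to be used only when MCS is tied to mortality, which is when dead MCS users weigh most under carry-forward coding. The subsection's stated aim is an accurate account of how MCS influences outcomes. Outcomes that exclude death plausibly include BARC 3B or higher bleeding, the key secondary safety endpoint, and heart failure.

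**Working it through.** **Plan figures.** The SAP gives no figure for this analysis. Its superiority sample size sets the trial size used in step 4, and it reproduces. For 50% vs 38%, two-sided 0.05, power 0.8, pooled variance under the null: n per arm = [1.960·√(2·0.44·0.56) + 0.8416·√(0.50·0.50 + 0.38·0.62)]² / 0.12² = (1.376 + 0.586)² / 0.0144 ≈ 267.4, so 268 per arm and 536 in total, as stated.

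**Assumptions, not in the SAP.** 25% of patients are MCS candidates; 30-day mortality without MCS is 45%; the non-fatal outcome has a 15% risk over 30 days in the absence of death; MCS multiplies the death hazard by 2 or 3; MCS has no effect on the outcome (true ratio 1.0). There is no other censoring before day 30.

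**Step 1: the mechanism at one time point.** Take MCS from day 0, mortality ratio 2, constant hazards, and look at day 15, ignoring the few who have already had the outcome. Alive without MCS: 0.75 × 0.55^0.5 = 0.556, dead 0.194. Alive with MCS: 0.25 × 0.55 = 0.1375, dead 0.1125. Only the living can have the outcome, at the same rate in both groups.
- Last value carried forward: apparent ratio = (0.1375/0.25) / (0.556/0.75) = 0.55/0.742 = 0.74.
- MCS set to 0 after death: all the dead join the MCS = 0 group, so apparent ratio = (0.556 + 0.194 + 0.1125)/0.556 = 1.55.
- Dead patients removed (cause-specific): 1.0.

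**Step 2: the whole 30 days in closed form, carried forward, MCS from day 0.** In units of 30 days the death hazard is d = −ln 0.55 = 0.598 and the outcome hazard is e = −ln 0.85 = 0.1625. Cumulative incidence = e/(e+d) × [1 − exp(−(e+d))].
- Without MCS: 0.1138.
- With MCS, death hazard 2d: 0.0889. Average subdistribution ratio = ln(1−0.0889)/ln(1−0.1138) = 0.77.
- With MCS, death hazard 3d: 0.0713. Ratio = 0.61.

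**Step 3: simulation with time-dependent MCS start.** With the 15% event risk and constant death hazard, carry-forward gives about 0.80 to 0.90 (mortality ratio 2) and 0.63 to 0.72 (ratio 3). Setting MCS to 0 after death gives 1.38 to 1.49. Cause-specific Cox gives 0.97 to 1.02.

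A wider set of runs (400,000 patients each, 10% event risk) varied the mean MCS start and the shape of the death hazard:

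| Death hazard | MCS mortality ratio | Carried forward, mean start day 0 / 0.5 / 2 / 5 | Set to 0 after death |
|---|---|---|---|
| Constant | 1 | 1.01 / 1.00 / 1.05 / 1.11 | 1.38–1.47 |
| Constant | 2 | 0.77 / 0.79 / 0.84 / 0.89 | 1.39–1.48 |
| Constant | 3 | 0.60 / 0.62 / 0.65 / 0.72 | 1.36–1.46 |
| Front-loaded | 1 | 0.99 / 1.12 / 1.26 / 1.37 | 1.67–1.74 |
| Front-loaded | 2 | 0.67 / 0.78 / 1.01 / 1.17 | 1.77–1.80 |
| Front-loaded | 3 | 0.45 / 0.55 / 0.78 / 0.97 | 1.75–1.81 |

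Cause-specific Cox returned 0.97 to 1.03 in every row. When deaths come early and MCS starts late, patients who die before MCS could begin are carried as non-users. This pads the comparison group and cancels or reverses the carry-forward effect.

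**Step 4: at trial size.** In 1,500 simulated trials of 536 patients (front-loaded death, mortality ratio 3, mean start half a day, two-sided 0.05), carry-forward gave a falsely protective result in 10% of trials at 10% event risk and 34% at 20%. Setting MCS to 0 gave a falsely harmful result in 23% and 39%. Across all trial-size runs, cause-specific Cox gave 0–2% protective and 2–4% harmful. At 5% event risk, falsely protective results under carry-forward were rare (at most about 2%), so the consequence depends on how common the outcome is.

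**The case against.** **The premise is an inference.** The Fine & Gray item lists no covariates, the only written equation is the Cox model, and the preceding sentence places the time-dependent variables within Cox. This is fair. But the item stands under the lead-in that sends these covariates into the listed models, its trigger is MCS, and no other covariate set is given. That makes it the plain reading, though not an explicit statement. The restriction to time-dependent Cox in Reporting & Interpretation does not settle it: the sentence concerns MACE curves and Fine & Gray is for non-MACE outcomes. Read broadly, it conflicts with the Fine & Gray item, and the text needs correcting anyway.

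**A subdistribution ratio below 1 is not always an error.** If MCS starts at day 0 and its users die more often, their cumulative incidence of the outcome really is lower. This stands. The error is to read that ratio as the influence of MCS on the outcome, which is the SAP's stated use.

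**Stronger readings a reader might infer.** One is that MCS will always look protective. The table contradicts this: the sign depends on the coding after death and on the timing of MCS and death. Another is that the treatment ratio from Fine & Gray is wrong if cangrelor lowers mortality. It is not: arm is fixed at randomization, and more survivors do mean a higher cumulative incidence of a non-fatal outcome.

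**The remedy is partial.** Cause-specific Cox removes the post-death coding problem, but treatment is still adjusted for a post-randomization variable. It returns 1.0 here because the simulation has no confounding between need for MCS and the outcome. This also stands.

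**Conclusion.** The concern holds as a defect of the model, with no fixed direction. On the plain reading, the SAP puts a covariate that ends at death into a model that keeps dead patients at risk, and gives no rule for its value there. With no true effect, the 30-day MCS ratio can fall to about 0.6 to 0.9 or rise to about 1.4 to 1.5 under constant death hazard, depending on a choice the SAP leaves open. Front-loaded death widens both ranges.

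These sizes rest on assumed MCS use, mortality ratios, event risks and timing. They apply to 30 days only; a one-year figure would need a death hazard after day 30 that the SAP does not give. The analysis is conditional, and the endpoints are tested by chi-square with a Z-test for non-inferiority (Statistical analysis), so the primary result and the sample size are unaffected. It should be corrected before analysis because the correction is specific and cheap.

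**What to change.** In Handling of Post-Randomization Events (MCS), for outcomes that exclude death:

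- Estimate the time-dependent MCS association with cause-specific Cox models, one for the outcome and one for death, with patients leaving the risk set at death. Report it as an association, since need for MCS may be confounded with the outcome.
- Show Aalen-Johansen cumulative incidence by randomized arm, with death as the named competing event.
- Restrict Fine & Gray, if used, to randomized arm and pre-randomization covariates.
- List the outcomes concerned, and align the restriction under Reporting & Interpretation with these models.

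The cost is SAP wording and one extra model per outcome. Cause-specific ratios do not translate directly into absolute risk, which is why the cumulative incidence display is needed beside them.
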